4.3.6 Subgroup analyses

An ANCOVA model similar to that described for the primary analysis in [Section 4.3.2](#) will be performed for each of the following subgroups, including a treatment-by-subgroup interaction term (if the minimum number of participants in each subgroup is at least 20):

- Age (<65 years; \geq 65 years)
- Baseline HbA1c (<8.5%; \geq 8.5%)

- SGLT-2i use (yes; no)
- GLP-1 RA use (yes; no)
- SU use (yes; no)
- eGFR
 - $<45 \text{ mL/min/1.73 m}^2$; $\geq 45 \text{ mL/min/1.73 m}^2$
 - $15 - <30 \text{ mL/min/1.73 m}^2$; $\geq 30 - <45 \text{ mL/min/1.73 m}^2$; $\geq 45 - 60 \text{ mL/min/1.73 m}^2$

The treatment effects (Gla-300 vs IDeg-100) across the subgroups defined for each of these factors will be estimated for the change from baseline to Week 24 in HbA1c values for the ITT population. The ANCOVA model will include a treatment-by-subgroup interaction term and a subgroup term, in addition to the following covariates which are included in the model used for primary endpoint analysis: baseline HbA1c value, study drug treatment, SU use (Yes, No), and eGFR ($<45 \text{ mL/min/1.73 m}^2$; $\geq 45 \text{ mL/min/1.73 m}^2$). In the case that the subgroup factor is identical or similar to other factor(s) in the model, those factors will be excluded from the model and the subgroup factor will be used exclusively. If the ANCOVA model does not converge, randomization strata may be removed from the model.

The mean difference in change from baseline to Week 24 in HbA1c values between treatment arms (Gla-300 vs IDeg-100) will be estimated based on the least-squares (LS) means in the model for each subgroup level. The estimated treatment means differences and their SEs obtained across the imputed datasets will be combined via SAS PROC MIANALYZE to produce a single point estimate difference along with a 2-sided 95% CI (Wald) all based on Rubin's rules. In addition, the p-value of the treatment-by-subgroup interaction will be presented.

In addition to the analyses described above, a forest plot will be presented for each of the subgroup analyses listed above and will present the number, the LS means differences (SE) between treatments and their associated 2-sided 95% CIs. The p-value of the treatment-by-subgroup interaction will also be presented.

Further subgroup analyses may be performed if deemed necessary for interpretation of results.

4.4 SECONDARY ENDPOINTS ANALYSIS

4.4.1 Secondary endpoints

4.4.1.1 *Definition of endpoints*

- **Change from baseline to Week 24 in fasting plasma glucose (FPG):** blood samples will be collected to measure FPG levels at the central laboratory at the time points specified in [Section 5.7](#). For scheduled site visits, participants will be required to arrive having fasted (no intake of food or drink, except water, in the 8 hours before blood sampling) without administering the study drug.

- **Change from baseline to Week 24 in fasting SMPG:** participants will be required to measure fasting SMPG values (using the glucose meter supplied during the screening period) before breakfast and before administration of the study drug once daily throughout the treatment period; results will be recorded in the participant's electronic diary (eDiary). Additional glucose measurements may be done at the investigator's discretion. Fasting SMPG measurements will be averaged for over the 7-day window preceding the date of each participant's Week 12 and Week 24 site visit and will be considered missing if there are less than 4 days of SMPG measurements in the week preceding the visit. Baseline values will not be based on a weekly average and will instead be identified as described in [Section 4.1](#).
- **Change from baseline to Week 24, per time point within 24-hour period in 7-point SMPG profiles:** the 7-point SMPG profile will be measured using the participant's glucose meter and recorded in the eDiary at the following 7 points: pre-prandial breakfast, 2 hours after breakfast, pre-prandial lunch, 2 hours after lunch, pre-prandial dinner, 2 hours after dinner and at bedtime. Timepoints are specified in the [Section 5.7](#). The 7-point SMPG profile will be performed over a single 24-hour period, on at least two days within the week before selected site visits. The records for each time point will be averaged for Week 12 and Week 24 measurements (including measurements taken on the 7 days preceding the visit). If less than 2 days of measurements (a 'day' being a 24-hour period including each time point) are completed for a time point, the SMPG value will be considered missing for that time point. Baseline values will not be based on a weekly average and will instead be identified as described in [Section 4.1](#).
- **Percentage (%) of participants reaching HbA1c target of <7.0% at Week 24:** blood samples will be collected to measure HbA1c at the different time points specified in the [Section 5.7](#). The number and percentage of subjects reaching the HbA1c target of <7.0% at Week 24 will be presented. If a participant has a missing HbA1c value at Week 24, it will be assumed that they did not reach an HbA1c target of <7.0%.

4.4.1.2 Main analytical approach

All secondary endpoints will be analyzed for the ITT set.

The continuous secondary endpoints described above will be analyzed using the same main analytical approach as described for the primary endpoint in [Section 4.3.2](#). Missing data will be multiply imputed as described in [Section 4.3.2](#) for the primary endpoint analysis. The imputation model for Step 1 will use the corresponding baseline continuous endpoint value as a covariate, and continuous endpoint values at Week 12 and 24 as variables; the imputation model for Step 2 will additionally include all stratification factors at randomization (categorized baseline HbA1c value ([8.5%, ≥8.5%], SU use [yes, no], and eGFR [<45 mL/min/1.73 m²; ≥45 mL/min/1.73 m²]).

Following imputation of missing data, an ANCOVA model will be performed for each imputed data set; this analysis will include the continuous baseline secondary endpoint value as a covariate, study drug treatment, and randomization strata (categorized baseline HbA1c value [<8.5%, ≥8.5%], SU use [yes, no] and eGFR [<45 mL/min/1.73 m²; ≥45 mL/min/1.73 m²]) as fixed factors. The difference in mean change from baseline to Week 24 in each continuous

secondary endpoint's values between treatment arms (Gla-300 vs IDeg-100) will be estimated based on the difference of LS means in each ANCOVA model. The estimated differences and associated SEs obtained across the imputed datasets will be combined via SAS PROC MIANALYZE to produce a single point estimate difference along with a 2-sided 95% CI (Wald) and nominal 2-sided p-value, all based on Rubin's rules.

Box plots based on OC will also be produced for each of the continuous endpoints from baseline to Week 24, other than the 7-point SMPG profile data, for which a line plot of mean and standard error will be plotted for each time point.

For the categorical secondary endpoint (participants reaching HbA1c target of <7.0% at Week 24), a logistic regression model with terms of treatment arm, stratification at randomization (SU) use (Yes, No), and eGFR (<45 mL/min/1.73 m²; ≥45 mL/min/1.73 m²), and HbA1c value at baseline will be performed. If a patient has a missing HbA1c value at Week 24, the endpoint will be imputed, and it will be assumed that they did not reach an HbA1c target of <7.0%. The adjusted odds ratio (OR) estimated from the model will be presented together with a 2-sided 95% CI and nominal 2-sided p-value.

[figure not shown]
A bar chart based on OC will also be presented that displays the frequency and percent of participants reaching the HbA1c target of <7.0% at Week 24 by treatment arm.

Note that if superiority is achieved for the primary endpoint (change from baseline to Week 24 in HbA1c level), the p-values for each secondary endpoint described as 'nominal' above will be assessed for superiority. To address the issue of Type I error related to multiple testing, the Holm procedure will be used to control the overall family-wise Type I error rate as described in [Section 4.6](#).

4.5 TERTIARY/EXPLORATORY ENDPOINTS ANALYSIS

4.5.1 Definition of endpoints

Exploratory:

CCI

CCI

[figure not shown]
CCI

CCI

4.5.2 Main analytical approach

Exploratory endpoints:

CCI

CCI

CCI

4.6 MULTIPLICITY ISSUES

There is no multiplicity argument that affects switching between non-inferiority and superiority in analysis of the primary endpoint, since it corresponds to a simple closed testing procedure.

If superiority is achieved for the primary endpoint (change from baseline to Week 24 in HbA1c level), superiority will be assessed for the key secondary endpoints defined in [Section 4.4.1.1](#). To address the issue of multiple testing, the Holm procedure will be used to control the family-wise Type I error rate:

- Let α be the significance threshold for rejecting the null hypothesis and m be the number of hypotheses.
- Order m hypotheses (H_1, H_2, \dots, H_m) by their respective p -values (p_1, p_2, \dots, p_m) from lowest to highest.
- If $p_1 < \frac{\alpha}{m}$, reject the null hypothesis; otherwise, all null hypotheses should be accepted and testing should be stopped.
- Repeat this process until $p_k < \frac{\alpha}{m+1-k}$, where k represents the first p -value that is not low enough to reject the null hypothesis H_k , at which time all remaining null hypotheses H_1, \dots, H_{k-1} are non-significant and should not be rejected.

No multiplicity adjustment will be made on the exploratory efficacy endpoints (including the CGM substudy endpoints), nor for subgroups. When presented for these analyses, 95% CIs, will be provided for descriptive purpose only.

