4 STATISTICAL ANALYSES

4.1 GENERAL CONSIDERATIONS

Due to early termination of the study, the analyses described in this SAP were not performed in totality due to lack of data and in accordance with the abbreviated CSR (clinical study report). See Appendix 2 ([Section 5.2](#)): Changes to protocol-planned analyses for additional details.

In general, continuous data will be summarized using the number of observations available, mean, SD, median, Q1, Q3, minimum, and maximum.

All mean, SD, median, Q1 and Q3 values will be formatted to one more decimal place than the measured value. Minimum and maximum will be formatted to the same number of decimal places as the measured value.

Categorical data will be summarized using frequency counts and percentage of participants. When count data are presented, the percent will be suppressed when the count is zero to draw attention to the non-zero counts. A row denoted 'Missing' will be included in count tabulations for demographics, baseline characteristics and compliance to account for missing values. No percentages will be displayed on the 'Missing' rows and the percentages on the other rows will be based on the number of non-missing observations. Unless otherwise specified, the denominator for all other percentages will be the number of participants in that treatment within the specific analysis set of interest. All percentages will be rounded to one decimal place. The number and percentage of responses will be presented in the form xx (xx.x), where the percentage is in the parentheses. When the numerator is equal to the denominator, the percentage should be presented as (100) instead of (100.0), unless otherwise specified.

All CIs presented will be 2-sided 95% CIs, unless otherwise specified, and will be displayed to the same level of precision as the statistic they relate to. If an estimate or a CI is not estimable, it will be presented as 'NE'. If neither an estimate, nor its CI are estimable, it will be presented as simply 'NE', not displaying 'NE' twice.

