- Step 2 will test superiority of Gla-300 versus IDeg-100 if noninferiority of Gla-300 versus IDeg-100 as described above has been demonstrated. The superiority of Gla-300 versus IDeg-100 will be established if the 95% CI for the difference in mean change from baseline to Week 24 in HbA1c level between Gla-300 and IDeg-100 lies entirely below 0%. If non-inferiority has been established but the superiority is not met, the declaration of non-inferiority will be further supported by a supplementary estimand as described in [Section 4.3.4](#).

There is no multiplicity argument that affects switching between non-inferiority and superiority in the analysis of the primary endpoint, since both are based on the same estimand and it therefore corresponds to a simple closed testing procedure. If superiority for the primary endpoint (change from baseline to Week 24 in HbA1c level) is achieved, secondary endpoints will be assessed for superiority and adjusted for Type I error related to multiple testing using the Holm procedure as described in [Section 4.6](#). Control of Type I error will be limited to the primary and key secondary efficacy endpoints for the overall population. No statistical claim will be made on the exploratory efficacy endpoints (including the CGM substudy endpoints), nor for subgroup analyses.

All safety analyses will be performed on the safety set.

In general, descriptive statistics of quantitative efficacy and safety parameters (result and absolute change from baseline) by analysis visits will be provided on observed cases (OC; ie, inclusion of only participants having non-missing assessments for a specific analysis visit). Descriptive summaries of continuous efficacy and safety data at baseline will be included when presenting descriptive summaries of the corresponding changes from baseline, where appropriate. Unless otherwise specified, analyses will be performed by intervention group (and overall for baseline and demographics characteristics).

Despite the open-label administration of the study drugs, all statistical analyses outlined in this plan prior to final database lock will be developed and performed blindly. A process will be

applied to ensure blinding of Gla-300 and IDeg-100 administrations and any potentially unblinding information.

All statistical analyses will be performed using SAS software Version 9.4 or higher.

Observation period

The observation period will be divided into 3 segments for non-safety analyses:

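### Does the misprinted last step of the Holm procedure in SAP 4.6 need correcting, given that no Holm test will be run?

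*SAP*

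**What the plan says.** SAP 4.6 opens a family of secondary hypotheses once superiority is shown on the primary endpoint. It names Holm's procedure, orders the p-values from smallest to largest, and compares the smallest with α/m. The last bullet covers the later steps. It continues until p_k < α/(m+1−k), and describes k in words as the first p-value "not low enough to reject the null hypothesis" H_k. It then concludes, "at which time all remaining null hypotheses" H_1, …, H_(k−1) "are non-significant and should not be rejected".

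The family is described in three places:

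- SAP 4.1: "Control of Type I error will be limited to the primary and key secondary efficacy endpoints".
- SAP 4.4.1.1 lists four secondary endpoints and marks none of them as key: FPG, fasting SMPG, the 7-point SMPG profile, and HbA1c below 7.0%. The profile is defined as change to Week 24, "per time point within 24-hour period in 7-point SMPG profiles".
- SAP 4.4.1.2 gives each continuous endpoint an ANCOVA estimate with a "2-sided 95% CI (Wald) and nominal 2-sided p-value". It puts the p-value of every secondary endpoint into the family, where "the Holm procedure will be used to control the overall family-wise Type I error rate".

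Protocol 8.7.1 planned no multiplicity adjustment for secondary endpoints. SAP Appendix 2 (5.2) lists the adjustment as a change from the protocol.

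On what was actually done, SAP 4.1 says that because of early termination "the analyses described in this SAP were not performed in totality due to lack of data". Appendix 2 reduces primary and secondary efficacy to descriptive summaries, and Appendix 6 (5.6) lists the outputs.

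**The concern.** A testing rule should be executable as written, and this one is not. The inequality is the condition for rejecting, but the words define k by failure to reject, so no k satisfies both. The index range then points to the hypotheses that passed earlier steps, which reverses their verdict.

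Knowing Holm's procedure does not by itself settle the second gap. SAP 4.6 defines m only as the number of hypotheses. Counting endpoints gives 4; counting p-values gives 10. The first threshold is 0.0125 in one case and 0.005 in the other, so the same smallest p-value could be significant under one count and not under the other. Section 4.6 is the only place where the rule behind the SAP's claim of Type I error control for secondary endpoints is set out.

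**Working it through.** **Inputs.** The SAP gives no number for the Holm α. I assume 0.05 two-sided, from the 95% confidence intervals (SAP 4.1) and the 2-sided secondary p-values (4.4.1.2). The endpoints are those of 4.4.1.1. The p-values below are illustrative.

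**The last bullet.** With m = 4 the thresholds 0.05/(5−k) are 0.0125, 0.0167, 0.025 and 0.05. Take ordered p-values 0.001, 0.010, 0.030 and 0.200.

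- *Standard Holm.* 0.001 < 0.0125 and 0.010 < 0.0167, so H_1 and H_2 are rejected. 0.030 ≥ 0.025, so testing stops at k = 3 and H_3 and H_4 are retained.
- *Printed inequality as the stopping rule.* It is already true at k = 1, where the range H_1 to H_(k−1) is empty. If the repetition starts at k = 2, it is true there as well, and H_1 is called non-significant although the previous bullet rejected it.
- *Verbal k with the printed range.* k = 3, and H_1 and H_2 are called non-significant, the reverse of the correct result.
- *Words without the two faulty symbols.* H_3 is the first that cannot be rejected, and all remaining hypotheses (here H_4) are retained. This is standard Holm.

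The error therefore lies in one inequality sign and one index range. Both were read here from text extracted from the PDF, so they should be checked against the page. Other symbols in the extracted SAP are also damaged. The eGFR equation has exponent −1.200 in 4.7.4.1 but −β in the schedule footnote, 4.3.2 has a threshold with the 45 missing, and 4.4.1.2 has an HbA1c category with its less-than sign missing.

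**Family size.** FPG (1) + fasting SMPG (1) + SMPG profile (7 time points) + HbA1c below 7.0% (1) = 10 p-values. Counting the profile once gives 1 + 1 + 1 + 1 = 4, but that needs a single p-value for the profile, and 4.4.1.2 defines no joint test. Since 4.6 orders hypotheses by their p-values, only m = 10 can be run from the SAP.

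- First threshold: 0.05/4 = 0.0125, or 0.05/10 = 0.005. The count would change the first-step verdict for a smallest p-value from 0.005 to just under 0.0125.
- Worst misuse, 0.0125 applied to each of ten independent tests with all nulls true: 1 − (1 − 0.0125)^10 = 0.118.
- With m = 10: 1 − (1 − 0.005)^10 = 0.049.

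Correlation reduces the misuse figure. By simulation of two-sided normal tests, with the seven profile tests correlated at 0.3, 0.5 or 0.8 and the other three independent, it is 0.112, 0.102 or 0.079. With all ten equally correlated at those values it is about 0.11, 0.09 and 0.05. Correlation across all ten is more realistic, since fasting SMPG and the pre-breakfast profile point measure nearly the same thing. The correlations are assumed.

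**Whether the rule will be used.**

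| Item | Source |
|---|---|
| Trial terminated 27 June 2023 | SAP 1.1 |
| SAP approved 17 October 2023 | SAP Table 1 |
| Primary and secondary efficacy descriptive only | SAP 5.2 |
| Efficacy outputs: baseline summaries, observed-case plots and a listing of Week 24 values; no ANCOVA, logistic model or p-value table | SAP 5.6 |

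Holm testing starts only after superiority on the primary endpoint. No output tests that, so the secondary family is never opened.

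**The case for a change.** The best argument for a change is that the sponsor chose to add this adjustment and to claim error control, so the only text that specifies it should be right. The repair would cost one bullet and a sentence listing the hypotheses. The family size is more than a typing matter, since anyone who later ran the tests could choose m after seeing the p-values. A misread inequality sign would also not explain the wrong index range.

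Much of this stands. The bullet is wrong as extracted, no value of m or α is stated, and SAP 4.1 and 4.6 speak of key secondary endpoints without marking any. Two parts are weaker. H_k to H_m are not left without a verdict, because the words say that H_k cannot be rejected and that all remaining hypotheses are retained. And the 0.118 comes from applying 0.05/4 to ten tests, which the SAP nowhere proposes. What does not stand is the need to act. A corrected bullet would alter no planned output, and a note that Holm is not applied would largely repeat SAP 4.1 and Appendix 2.

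**Conclusion.** The last bullet of SAP 4.6 contains a clerical slip in a correctly named procedure. A statistician would read it as standard Holm: stop at the first k with p_k ≥ α/(m+1−k), reject H_1 to H_(k−1), and retain H_k to H_m. The family would be taken as ten hypotheses, because the SAP produces ten p-values and no combined profile test.

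No change follows, because there is nothing to gain. The effect on planned results is nil: the SAP was approved after termination, efficacy is descriptive, and no secondary p-value is in the output list. This rests on Appendix 2 and Appendix 6 being followed. If the full inferential plan were ever revived, or this text reused elsewhere, the bullet and the family size would have to be settled before any p-value was seen. The α of 0.05 two-sided is inferred, and the error rates above illustrate a misuse that is not planned.

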4.7 SAFETY ANALYSES

All safety analyses will be performed on the safety population as defined in [Section 3](#), unless otherwise specified, using the common rules:

- The analysis of the safety variables will be essentially descriptive, and no formal hypothesis testing is planned.
- Safety data in participants who do not belong to the safety population (eg, exposed but not randomized) will be provided separately.

The observation period of safety data will be divided into 3 periods as defined below:

- **Pre-treatment period:** the time between the date of signed informed consent and the first injection of the open-label study drug.
- **On-treatment period:** the time from the first injection of the open-label study drug up to 7 days after the last injection of the open-label study drug, regardless of the introduction of rescue therapy. The 7-day interval is chosen based on the half-life of the study drug (approximately 5 times the half-life of IDeg-100).
- **Post-treatment period:** the time starting 8 days after the last injection of the open-label study drug.

The denominator for computation of percentages is the safety set within each treatment arm unless otherwise specified.

